1.1 Synopsis

Name of Sponsor/Company: Clexio Biosciences Ltd.	Name of Study Treatment: CLE-400 or Vehicle	Name of Active Ingredient: Detomidine HCl monohydrate
Title of Study: A Randomized, Double-blind, Vehicle-controlled, Multicenter, Parallel-Design, Phase 2 Study to Assess the Efficacy and Safety of CLE-400 Topical Gel for the Treatment of Chronic Pruritus in Adult Subjects with Notalgia Paresthetica		
Phase of Development: Phase 2		
Study Centers: This study will be conducted at [REDACTED] study centers located in the United States.		
Number of Subjects (planned): Approximately 54 subjects are planned to be randomized in this study (approximately 27 subjects/arm).		
Duration of Study: The maximum study duration per subject is approximately 11 weeks, including up to 37 days for the screening period (including a 7-day run-in period), 4 weeks for the treatment period, and 2 weeks for the follow-up period.		
Study Treatments, Dosage, and Mode of Administration: CLE-400 gel will be provided at a concentration of 0.28% (w/w). Matching vehicle gel (active ingredient -free vehicle) will also be provided. [REDACTED] [REDACTED] Subjects will be randomized in a 1:1 ratio on Day 1 to CLE-400 gel 0.28% or vehicle. CLE-400/vehicle gel will be administered topically once daily (QD) for 4 weeks on the affected skin area located in the scapular/mid back region (application by a caregiver or self-application). Study treatment should be applied in the morning (at approximately the same time every day \pm 1 hour, except for applications during on-site visits). During study visits conducted on-site, the study treatment will be administered under the supervision of the study staff. The maximal amount of study treatment to be applied will be determined on Day 1 based on the size of the affected skin area, and the same area will be treated with the study treatment throughout the treatment period. [REDACTED]		

Name of Sponsor/Company: Clexio Biosciences Ltd.	Name of Study Treatment: CLE-400 or Vehicle	Name of Active Ingredient: Detomidine HCl monohydrate

Objectives and Endpoints:

OBJECTIVES	ENDPOINTS
Primary Objective	

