
This is a Phase 2, multicenter, randomized, vehicle-controlled, double-blind, parallel-group study to assess the efficacy, safety, and tolerability of CLE-400 for the treatment of chronic pruritus in adult subjects with notalgia paresthetica (NP). This study will also evaluate the plasma concentrations of detomidine in subjects with chronic pruritus associated with NP.
				

This study will include approximately 54 male and female subjects, aged 18 to 80 years (inclusive), with the following disease characteristics:
				

 Diagnosis of NP based on localized pruritus in a circumscribed, unilateral area in the scapular/mid-back region, with or without pigmentation changes. Chronic pruritus for ≥ 3 months prior to the screening visit. Weekly mean of the daily 24-hour Worst Itch-Numeric Rating Scale (WI-NRS) score ≥ 5.0 and ≤ 9.5 and a WI-NRS score ≥ 5 on at least 3 days over the 7-day run-in period. 				

The study will consist of an up to 37-day screening period (including a 7-day run-in period), a 4-week treatment period, and a 2-week follow-up period. For scheduled visits, subjects will come to the study center on up to 9 occasions: screening, Day 1, Day 3, Week 1, Week 2, Week 3, Week 4, and follow-up at Week 5 and Week 6 (Week 6 visit may be remote if there is no safety concern).
				

All subjects will read and sign an informed consent form (ICF) prior to any screening procedures being performed and will then undergo screening for study eligibility. To be eligible to participate in the study, subjects will also complete a 7-day run-in period (from Day -7 to Day -1) during which they will be required to complete daily WI-NRS assessments in an electronic diary (e-diary). For consistency, subjects will be requested to complete the WI-NRS at a similar time each evening. Subjects will also record the pain Numeric Rating Scale (NRS; each evening) and the sleep quality NRS (each morning) in their e-diary daily during the run-in period.
				

After a screening period of no more than 37 days (including the 7-day run-in period), eligible subjects will be randomized in a 1:1 ratio at Day 1 to treatment with CLE-400 gel 0.28% or
				

Name of Sponsor/Company: Clexio Biosciences Ltd.	Name of Study Treatment: CLE-400 or Vehicle	Name of Active Ingredient: Detomidine HCl monohydrate

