vehicle, administered topically QD for 4 weeks. During the 4-week treatment period, the study treatment will be applied QD to the affected skin area. For each subject, the site staff will determine the amount of gel to be applied based on the size of the affected skin area. The site staff will inform the subject on the amount of gel to apply daily.		
[REDACTED]		
[REDACTED] Study treatment should be applied in the morning (at approximately the same time every day \pm 1 hour, except for applications during on-site visits). During study visits within the treatment period, the study treatment will be administered under the supervision of the study staff		
[REDACTED]		
Subjects will be instructed to refrain from driving or operating heavy machinery if they observe an effect of the study treatment on their ability to drive or operate heavy machinery. When ESS is assessed at home, subjects will be instructed to report to the site staff if the total score is ≥ 16 . Subjects will also be instructed on recognition of symptoms that may be related to changes in blood pressure (BP) and heart rate (HR), fall precautions (preventive precautions and guidance on pre-fall symptoms), and on contacting the site as relevant.		
Efficacy will be assessed using WI-NRS, pain NRS, sleep quality NRS, Itching Quality of Life (ItchyQoL), Patient Global Impression of Itch Change (PGI-C), and Patient Global Impression of Itch Severity (PGI-S). Subjects will report their WI-NRS over the previous 24 hours every day from the start of the run-in period through the 4-week treatment period. The pain NRS and sleep quality NRS will be reported by the subject every day during the run-in period and during the 4th week of treatment. The Patient Health Questionnaire 8 (PHQ-8) will be assessed at the screening visit only as part of eligibility evaluation. A Study Participant Survey will be completed at Week 5.		

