Safety will be assessed by collecting adverse events (AEs), performing local tolerability assessments (LTAs), recording vital signs, performing physical examinations and electrocardiograms (ECGs), evaluating clinical laboratory results, and collecting Epworth Sleepiness Scale (ESS) scores. Assessments of BP, pulse, and ECGs will be performed pre-dose at every study visit. On Day 1, BP (systolic and diastolic) and pulse will also be recorded post-dose before the subject is discharged. BP and pulse measurements at rest will be performed in triplicate and will be followed by a measurement of orthostatic changes. Electrocardiograms will be assessed in triplicate. ESS scores will be reported by study subjects at each specified visit (predose), as well as at home in the first week on day 5, and in the following treatment weeks once at mid-week.		

Name of Sponsor/Company: Clexio Biosciences Ltd.	Name of Study Treatment: CLE-400 or Vehicle	Name of Active Ingredient: Detomidine HCl monohydrate
Blood samples will be collected from all subjects to evaluate pre-dose plasma concentrations of detomidine on Day 1, Day 3, Week 1, Week 2, and Week 3, and at any time during the visits on Week 4 (or early termination [ET], if applicable), Week 5, and Week 6 (if onsite).		
Inclusion/Exclusion Criteria:		
Inclusion Criteria:		
In order to be eligible to participate in this study, a subject must meet all of the following criteria, either at the screening and Day 1 visits or only at one of the specified visits (screening or Day 1) as noted in the criterion:		

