
The Safety Analysis Set includes all subjects who receive at least 1 dose of study treatment.
		

The ITT Analysis Set will be used for summaries of subject demographics and baseline variables.
		

Name of Sponsor/Company: Clexio Biosciences Ltd.	Name of Study Treatment: CLE-400 or Vehicle	Name of Active Ingredient: Detomidine HCl monohydrate
The FAS Analysis Set will serve as the principal analysis set for efficacy inference.		
The Safety Analysis Sets will be used for analyses of safety variables.		
Efficacy Analyses:		
Efficacy will be evaluated on the basis of the FAS analysis set.		
For all WI-NRS endpoints (% change and change from baseline and proportion of subjects), the weekly mean of the 24-hour WI-NRS will be defined as the sum of the daily 24-hour WI-NRS score reported during a specific week of the study (e.g., Days 1 to 7, Days 8 to 14, Days 15 to 21, etc.) divided by the number of days with nonmissing scores for that week. For all WI-NRS endpoints, the baseline score will be defined as the average of all nonmissing daily 24-hour WI-NRS scores over the run-in period (Day -7 to Day -1); at least 4 completed WI-NRS assessments will be required during the run-in period.		

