For the primary efficacy endpoint, the percent change from baseline in weekly mean of daily 24-hour WI-NRS, the statistical model to be used for inference will be the Mixed Models Repeated Measures (MMRM) analysis using the SAS® MIXED procedure with the REPEATED subcommand. The model will include terms for treatment, categorical Week in study (1, 2, 3, and 4), treatment by week interaction, pooled sites, Baseline weekly mean WI-NRS and Baseline weekly mean WI-NRS by week interaction. The percent change from baseline in the weekly mean of daily 24-hour WI-NRS score will be the response variable in the model. The model derived least squares means of percent changes at Week 4 will be compared between the CLE-400 group and the vehicle group. The model will use the unstructured covariance matrix, the Restricted Maximum Likelihood (REML) estimation method, and the Kenward Roger adjustment method for the degrees of freedom. In the case that the model does not converge, the Maximum-Likelihood estimation method will be used instead of the default REML. If the model still does not converge, then a simpler covariance structure with fewer parameters will be used according to the following order: heterogeneous autoregressive (1), heterogeneous compound symmetry, autoregressive (1), and compound symmetry.		
Safety Analyses:		
Safety analyses will include TEAEs, LTA, laboratory tests, vital signs, ESS scores, and ECGs.		
No inferential statistics will be done on safety variables.		
Pharmacokinetic Analyses:		
Detomidine concentration data will be listed per subject and summarized by visit, dose and nominal timepoints using descriptive statistics.		

Name of Sponsor/Company: Clexio Biosciences Ltd.	Name of Study Treatment: CLE-400 or Vehicle	Name of Active Ingredient: Detomidine HCl monohydrate
Sample Size Consideration:		

The sample size was determined based on the following assumptions: a difference of 24% in the percent change from baseline to Week 4 in WI-NRS between CLE-400 and vehicle, a randomization ratio of 1:1, a standard deviation (SD) of 30%, a power of 81%, a 2-sided alpha level of 0.05, and an overall drop-out rate of 5%.
 
Under the above assumptions, the estimated number of subjects required for this study is 54 subjects (27 subjects per treatment arm).
		

SPONSOR:

Clexio Biosciences Limited

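### Does drawing the Week 4 plasma sample at any time in the visit spoil a summary by nominal timepoint?

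*Combined protocol and SAP*

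**What the plan says.** All of this is in the Synopsis (section 1.1) of the combined protocol and SAP.

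- **Sampling (Study Design).** At the five visits up to and including Week 3, starting with Day 1, the blood sample is a pre-dose one. For the remaining visits the rule is freer, and the sample is drawn "and at any time during the visits on Week 4 (or early termination [ET], if applicable), Week 5, and Week 6 (if onsite".
- **Analysis (Pharmacokinetic Analyses).** "Detomidine concentration data will be listed per subject and summarized by visit, dose and nominal timepoints using descriptive statistics". The endpoint is a secondary one, confined to subjects on active treatment. No pharmacokinetic parameter, test or between-visit comparison is named.
- **Application at visits (Study Treatments, Dosage, and Mode of Administration).** "During study visits conducted on-site, the study treatment will be administered under the supervision of the study staff".
- **Application at visits (Study Design).** "During study visits within the treatment period, the study treatment will be administered under the supervision of the study staff". Redacted text follows directly.
- **Visit list (Study Design).** The list ends with "Week 3, Week 4, and follow-up at Week 5 and Week 6".
- **Study weeks (Efficacy Analyses).** Weeks are counted as "Days 1 to 7, Days 8 to 14, Days 15 to 21, etc".

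**The concern.** A nominal timepoint is a planned time relative to dosing, and a sample allowed at any time in a visit has none. For Week 5 and Week 6 this is of no account, because treatment has ended. Week 4 is less clear. It is a study-centre visit listed apart from follow-up, and one sentence has gel applied at on-site visits generally. If gel is applied at Week 4, some subjects could be sampled about 24 hours after the previous application and others shortly after that day's. One summary row would then hold two kinds of measurement, and it would not be comparable with the pre-dose rows at Day 3 and Weeks 1 to 3. Early-termination samples add a smaller worry: they can fall at varying times since the last application, and the sampling sentence names them together with Week 4.

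Plasma concentration is a stated secondary objective, and the listing and descriptive summary are the only analysis given for it. A blurred Week 4 row would therefore be a real, if small, loss.

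**Working it through.** **1. Number of samples.** The planned arm size reproduces from the stated assumptions (difference 24, SD 30, power 81%, two-sided alpha 0.05):

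2 × [30 × (1.960 + 0.878) / 24]² = 25.17 per arm; 25.17 / 0.95 = 26.5, rounded up to 27, so 54 in total.

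The sample-size paragraph assumes "an overall drop-out rate of 5" per cent. In the CLE-400 arm:

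- Week 4 samples: 27 × 0.95 = 25.65, about 26.
- Early-termination samples: 27 × 0.05 = 1.35, about 1, and only if those who drop out attend that visit.

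**2. Is gel applied at the Week 4 visit?** Once daily for 4 weeks is 28 applications, Day 1 to Day 28. On the stated pattern, Week 4 is Days 22 to 28. The relevant statements are:

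| Statement in the synopsis | What it shows about Week 4 |
|---|---|
| Supervised application at on-site visits | Cannot decide it. Taken literally it also covers Week 5 and an on-site Week 6, after treatment has ended |
| Supervised application at visits in the treatment period | Neutral until the visit day is known: application if Day 28 or earlier, none if Day 29 or later |
| Week 4 listed apart from follow-up | Fits a last dosing visit or an end-of-treatment visit without a dose |
| BP, pulse and ECG pre-dose at every visit | Weak. It also covers screening and follow-up, where nothing is applied |
| Sampling rule: pre-dose to Week 3, then free timing for Week 4/early termination, Week 5 and Week 6 | Most simply read as no dose at Week 4, since pre-dose has no meaning at the visits it is grouped with |

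No statement says that gel is applied at Week 4. The one reading that needs no conflict between statements is that it is not.

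**3. Consequence under each reading.**

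- *Visit on Day 29 or later:* 0 of the 26 samples follow a same-day application. Only the roughly 1 early-termination sample has an open interval since the last application.
- *Visit on Day 28 or earlier, with application:* any of the 26 could be drawn before or after application.

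**4. Can the second case be sized?** Suppose a share *f* is drawn after application and the level is then *r* times the pre-dose level. The Week 4 mean becomes 1 + *f*(*r* − 1) times the pre-dose mean. With *f* = 0.50, *r* = 1 gives 1.00, *r* = 1.5 gives 1.25 and *r* = 2 gives 1.50. Both *f* and *r* are assumptions. The synopsis gives no half-life, absorption profile or visit length, so these figures reflect the values chosen and are not evidence about the trial.

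**5. What depends on the Week 4 row?** The summary keeps visits apart, so a mixed Week 4 row could not affect the four on-treatment pre-dose visits (Day 3, Weeks 1, 2 and 3). No accumulation analysis and no Week 3 versus Week 4 comparison is planned. The primary MMRM, the fixed-sequence testing, the sample size and the safety summaries do not use concentrations.

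**The case for a change.** The strongest case for acting is that it would cost almost nothing: one clarifying sentence and, at most, one extra table row. The sentence on application at on-site visits is too broad whatever happens at Week 4. If gel is applied at that visit, the Week 4 and early-termination samples would be the only scheduled ones able to show levels soon after application. Pooling them would hide that, and a per-subject listing does not repair a mixed summary row.

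Part of this stands. The broad sentence is loose, and the synopsis leaves both the Week 4 visit day and the dosing question open. But the narrower sentence in Study Design already supplies the missing limit, and the Week 4 day is the kind of detail a visit schedule gives. The schedule and the detailed pharmacokinetic section are not part of the text reviewed, and redacted text follows the supervised-application sentence. The plan therefore cannot be said to omit the answer.

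The extra row depends on a dosing event that the synopsis does not state. Taking early-termination values out of the Week 4 row presumes a pooling that is stated nowhere: the sampling sentence says when that sample is drawn, and the analysis sentence says only that results are summarised by visit. If an analyst did meet mixed samples, separating them in a descriptive table would be routine provided sampling and application times were recorded, and nothing in the synopsis suggests that they are not.

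**Conclusion.** No change to the plan is warranted. The observation about wording is accurate: Week 4 and early-termination samples have no fixed time within the visit, and the synopsis does not say whether gel is applied at Week 4. But no stated rule is shown to give a wrong result, and mixing of pre- and post-application samples is a possibility that the text does not establish.

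The most that could be affected is one descriptive row of about 26 samples, plus about 1 early-termination sample, at the planned 27 per arm and 5% drop-out. If the visit falls after Day 28, none of the 26 is affected. The size of any shift cannot be derived from the documents. No trial conclusion turns on it under either reading.

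What remains is an editorial check: the two sentences on supervised application and the sampling sentence should be read against the full schedule and reconciled if they differ. If the schedule shows no application at Week 4, the free sampling time can stand. No view is taken on whether gel should be applied at that visit.

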To evaluate the efficacy of CLE-400 for the treatment of chronic pruritus in subjects with NP	
Primary Efficacy Endpoint:
 
 Percent change from baseline in weekly mean of the daily 24-hour WI-NRS score at Week 4. 
Secondary Efficacy Endpoints:
 
 Proportion of subjects achieving \geq 4-point decrease from baseline in weekly mean of the daily 24-hour WI-NRS score at Week 4. PGI-C ratings at Week 4. 
Exploratory Efficacy Endpoints:
 
 Percent change from baseline in weekly mean of the daily 24-hour WI-NRS at Week 2. Change from baseline in weekly mean of the daily 24-hour WI-NRS at Week 4. Proportion of subjects achieving \geq 3-point decrease from baseline in weekly mean of the daily 24-hour WI-NRS score at Week 4. Change in PGI-S ratings from baseline to Week 4. Proportion of subjects achieving improvement (“Much improved” or “Very much improved”) according to the PGI-C at Week 4. Change from baseline in weekly mean of daily sleep quality NRS at Week 4. Change from baseline in weekly mean of daily pain NRS at Week 4. Change from baseline in ItchyQoL at Week 4.
Secondary Objectives	
To evaluate the safety and local tolerability of CLE-400 in subjects with chronic pruritus associated with NP	
Secondary Safety Endpoints:
 
 Incidence of TEAEs. Change from baseline in vital signs, clinical laboratory parameters, ECGs, and ESS. Local Tolerability Assessment (LTA).

Name of Sponsor/Company: Clexio Biosciences Ltd.	Name of Study Treatment: CLE-400 or Vehicle	Name of Active Ingredient: Detomidine HCl monohydrate		
To evaluate the plasma concentration of detomidine in subjects with chronic pruritus associated with NP	
Secondary PK Endpoints:
 
 Measurement of plasma concentrations of detomidine in subjects receiving active treatment. 			

Abbreviations: TEAE, Treatment Emergent Adverse Event; ECG, Electrocardiogram; ESS, Epworth Sleepiness Scale; ItchyQoL, Itching Quality of Life; LTA, Local Tolerability Assessment; NP, Notalgia Paresthetica; NRS, Numeric Rating Scale; PGI-C, Patient Global Impression of Itch Change; PGI-S, Patient Global Impression of Itch Severity; WI-NRS, Worst Itch Numeric Rating Scale.
				

Study Design:
				

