
Name of Sponsor/Company: Clexio Biosciences Ltd.	Name of Study Treatment: CLE-400 or Vehicle	Name of Active Ingredient: Detomidine HCl monohydrate

physical/laboratory/ECG/vital signs abnormality that would, in the opinion of the investigator, put the subject at undue risk or interfere with interpretation of study results.
		

32. Subject has received a nonbiological investigational product or device within 4 weeks prior to the run-in period (Day -7) or has received any investigational biological agent within 12 weeks or 5 half-lives (whichever is longer) prior to the run-in period (Day -7).
 
33. Planned major surgery during the clinical study.
 
34. Sponsor or CRO employees or employees under the direct supervision of the investigator and/or involved directly in the trial, or their family members/subjects in same household.
 
35. In the opinion of the investigator, the subject is unsuitable for participating in the study.
		

Statistical methods:
		

The significance level of this study will be 0.05, 2-sided.
 
A fixed sequence gatekeeping (hierarchical) approach will be applied to adjust for multiplicity and to control type I error due to multiple efficacy endpoints testing of the primary and secondary endpoints. The sequence order is according to the defined order of the primary and secondary endpoints. If the primary analysis is statistically significant at the 2-sided 0.05 level, the secondary endpoints will be analyzed sequentially according to the order of the secondary endpoints as listed above. A secondary endpoint will only be considered statistically significant at the 2-sided 0.05 level if the previous secondary or primary endpoint in the hierarchy is significant at the 2-sided 0.05 level.
 
.
		

Analysis sets:
		

The Intent-To-Treat (ITT) Analysis Set will include all randomized subjects. In this analysis set, treatment is assigned based on the treatment to which subjects were randomized, regardless of which treatment they actually received.
		

The Full Analysis Set (FAS), which is a subset of the ITT Analysis Set, will include all randomized subjects who received at least 1 dose of study treatment and have both baseline and at least one postbaseline WI-NRS evaluation. In this analysis set, treatment is assigned based on the treatment to which subjects were randomized, regardless of which treatment they actually received.
		

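### Should the first gated secondary, the ≥ 4-point WI-NRS responder rate, move from the FAS to all randomised subjects with missing Week 4 counted as non-response?

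*Combined protocol and SAP*

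**What the plan says.** All references are to the Combined protocol and SAP, section 1.1 Synopsis, which is the only part available here.

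- **Endpoint and order.** The first secondary efficacy endpoint is the proportion of subjects with at least a "4-point decrease from baseline in weekly mean of the daily 24-hour WI-NRS score at Week 4". PGI-C at Week 4 is second. Under Statistical methods, once the primary is significant, "the secondary endpoints will be analyzed sequentially according to the order of the secondary endpoints as listed above".
- **Analysis sets.** The FAS takes randomised subjects who "received at least 1 dose of study treatment and have both baseline and at least one postbaseline WI-NRS evaluation", analysed as randomised. Under Efficacy Analyses: "Efficacy will be evaluated on the basis of the FAS analysis set". The only use given for the full randomised set is descriptive: "The ITT Analysis Set will be used for summaries of subject demographics and baseline variables".
- **Weekly mean.** The rule opens "For all WI-NRS endpoints (% change and change from baseline and proportion of subjects", so it covers the responder endpoints. The weekly sum is "divided by the number of days with nonmissing scores for that week". The minimum of four completed assessments applies to the run-in only.
- **Model.** The MMRM is specified for the primary endpoint. The synopsis names no test for the responder rate or for PGI-C.
- **Dosing and diary.** "During study visits conducted on-site, the study treatment will be administered under the supervision of the study staff". Day 1 includes post-dose vital signs, and WI-NRS is recorded every evening.

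**The concern.** Two features look wrong together. First, membership of the FAS depends on receiving a dose and on making a diary entry, both after randomisation, while the set of all randomised subjects is defined but not used for efficacy. For a binary endpoint this changes the denominator. Second, if Week 4 (Days 22 to 28) has no scores, the weekly mean is zero divided by zero. The MMRM accommodates missing weeks for the primary, but nothing comparable is given for the responder rate.

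The stake is the gate. The responder test decides whether PGI-C can be declared significant, and with 27 per arm a few subjects can carry a borderline result across 0.05. A choice made after unblinding would be open to criticism. The natural proposal is to test all randomised subjects and count anyone without a Week 4 mean as a non-responder.

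**Working it through.** **The plan's own figure.** Inputs from Sample Size Consideration: difference 24, SD 30, two-sided alpha 0.05, power 81%, drop-out 5%.

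n per arm = 2 × (1.960 + 0.878)² × (30/24)² = 2 × 8.05 × 1.5625 ≈ 25.2, so 26. Total 52/0.95 = 54.7, so 55 against the stated 54. In reverse, 54 × 0.95 = 51.3, about 26 evaluable per arm, where a two-sample t-test has 80.7% power. The stated size reproduces closely. It concerns the primary endpoint only and does not bear on the responder test.

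**How many subjects are affected?**

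- *Outside the FAS.* Almost nobody should go undosed, and one evening entry keeps a dosed subject in. If 10% to 50% of the planned 5% drop-outs never make a post-baseline entry (assumption), the expected number is 54 × 0.005 = 0.27 to 54 × 0.025 = 1.35.
- *In or out of the FAS, with no Week 4 score.* If this equals the whole planned drop-out (assumption), 54 × 0.05 = 2.7 subjects, 95% range 0 to 6, with P(at least one) = 1 − 0.95⁵⁴ = 0.94. Someone who leaves during Week 4 after one entry still has a status; someone who stays but records nothing that week does not.

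**Can so few move a p-value?** Yes, at the boundary. Responder counts are assumed, since the synopsis gives no response rates.

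| CLE-400 | Vehicle | Pearson p | Fisher p |
|---|---|---|---|
| 13/27 | 6/27 | 0.046 | 0.086 |
| 13/26 (one non-responder dropped) | 6/27 | 0.035 | 0.047 |
| 13/27 | 6/26 (one non-responder dropped) | 0.057 | 0.086 |
| 14/27 | 7/27 | 0.051 | 0.093 |
| 14/24 (three dropped) | 7/27 | 0.019 | 0.025 |
| 14/27 | 7/24 (three dropped) | 0.100 | 0.154 |

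The direction depends on the arm the missing subjects come from, so the table shows sensitivity and not bias.

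**Does the alternative perform better?** Exact binomial sums with 27 per arm and 5% missing at random in each arm. "Dropped" leaves missing subjects out; "failure" counts them as non-responders out of 27. Response rates are assumed.

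| True rates (CLE-400 / vehicle) | Pearson power, dropped → failure | Fisher power, dropped → failure |
|---|---|---|
| 40% / 15% | 54.1% → 54.3% | 44.5% → 39.4% |
| 50% / 25% | 46.9% → 45.2% | 39.9% → 34.7% |
| 60% / 30% | 59.4% → 55.0% | 51.7% → 44.6% |

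Under the null, with common response rates of 15% to 30%, Pearson type I error is 0.053 with subjects dropped and 0.055 to 0.057 with failures counted. Fisher is at most 0.032 under either rule.

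**How often do the two rules disagree?** In the same scenarios, significance only with subjects dropped occurs in 1.9% to 5.7% of trials (Pearson) or 5.4% to 7.6% (Fisher). The reverse occurs in 1.3% to 2.1% or 0.2% to 0.5%. For Fisher the gap between the two is the power loss: at 40%/15%, 5.36% − 0.22% = 5.1 points, matching 44.5% − 39.4%.

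**Unequal missingness.** With 7.5% missing on CLE-400 and 2.5% on vehicle, significance only with subjects dropped rises to 4.7% to 11.2% (Pearson) or 10.6% to 14.0% (Fisher). With the split reversed, significance only under failure counting occurs in 4.0% to 5.3% or 1.1% to 2.1%. Counting failures is therefore not reliably conservative: it favours CLE-400 when vehicle subjects are the ones missing.

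**The case for a change.** The strongest argument for a change is that it costs a sentence or two and needs no new data. A binary endpoint that gates another should have a fixed denominator and a status for every subject, set before unblinding. About 94% of trials of this size would have at least one subject without Week 4 scores if the planned drop-out holds, so the case is not remote. The primary has a model that copes with missing weeks; the first secondary has nothing stated.

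Much of this stands as description. The synopsis text leaves the status undefined, and how these subjects are counted should be settled before the blind is broken. Two parts do not stand. The case against the FAS falls on its own numbers, because about one subject or fewer is expected to be affected; the subjects who matter are mostly already in the FAS, and a change of analysis set would give them no status. And the absence of a rule is shown only for a synopsis that also omits the test itself for both secondaries. That level of detail normally sits in the statistical section of the protocol body or in the SAP, so its absence from a summary does not show that the plan lacks it.

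**Conclusion.** No change follows. The FAS is clearly defined, analysed as randomised and applied to all efficacy; replacing it with ITT would affect about 0.3 to 1.4 expected subjects of 54 and would put the primary and first secondary on different sets. The undefined status for subjects with no Week 4 scores, about 2.7 expected at most if only the planned 5% drop-outs are affected, is a gap that analysts fill with a standard convention when they specify the test. The particular convention proposed is a fair trade-off and not a correction: no better type I error, 5 to 7 points less power by Fisher and 0 to 4 by Pearson, and an effect in either direction when missingness is unequal. The practical consequence is also narrow, since it arises only if the primary is significant and the responder result is borderline, and the one gated endpoint left is PGI-C in a Phase 2 trial.

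These sizes rest on assumed response rates (40% to 60% against 15% to 30%), drop-out equated with having no Week 4 scores, and missingness at random within arm. The synopsis gives only the 5% overall drop-out. Heavier or clearly lopsided loss before Week 4 would make the choice of convention matter more, but would not by itself show which one is right.
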